5.2 Visit Windows

The follow-up schedule and analysis windows are listed below.

- Discharge visit (discharge or 7 days post-procedure, whichever comes first)
- 30-Day Visit \pm 7 Days [23, 37 days]
- 6-Month Follow-up (180 \pm 30 days) [150, 210 days]
- 12-Month Follow-up (365 \pm 45 days) [320, 410 days]
- 2 years (730 days) \pm 45 days [685, 775 days]
- 3 years (1095 days) \pm 45 days [1050, 1140 days]
- 4 years (1460 days) \pm 45 days [1415, 1505 days]
- 5 years (1825 days) \pm 45 days [1780, 1870 days]

6. STATISTICAL ANALYSIS

6.1 General Conventions

- For continuous variables, data will be summarized using the number of observations, mean, median, standard deviation, minimum, maximum, and 95% confidence intervals (based on normal distribution) per table shells. Nonparametric techniques may be used if the data

 Edwards Lifesciences	Revision Date: January 22, 2019		Rev 	For Use Only by Affiliates of Edwards Lifesciences	Page 15 of 25
	Title	Statistical Analysis Plan for Edwards CLASP TR EFS			

does not meet the assumptions of parametric tests.

- For categorical variables, data will be summarized using the number of observations, percentage, and 95% Clopper-Pearson confidence intervals per table shells. In general, the denominator for the percentage calculation will be based on total number of patients with evaluable data for a specified time point unless otherwise specified. Patients with missing data will be excluded from the denominator.
- For time-to-event variables, survival analysis will be used to analyze the data. Summaries will include the number of patients at risk, and number of patients with the event. Patients without events will be censored at their last known event-free time point. If this event-free time point occurs after the analysis time point, the days to event variable will be set equal to the analysis time point so that the patient will be included in the analysis. For patients who did not have an event or early withdrawal and have not yet completed the analysis visit, they will be censored at their last information date. Time to first event curves will be constructed using Kaplan-Meier estimates and all post procedure results will be summarized with Kaplan-Meier estimates of event rates. Hazard ratios, confidence interval for the hazard ratios, and p-values may also be presented from a Cox proportional hazards model.
- For selected variables, in addition to descriptive summary statistics at each follow-up assessment, change from baseline to subsequent time point will be summarized. Paired (i.e., patients with available data at both baseline and respective time point) and unpaired data will be presented separately for selected variables. In general, patients with missing baseline or following-up values will be excluded from the analysis unless otherwise specified.

 Edwards	Revision Date: January 22, 2019		Rev	 For Use Only by Affiliates of Edwards Lifesciences	Page 16 of 25
	Title	Statistical Analysis Plan for Edwards CLASP TR EFS			

- If insufficient data are available for summary statistics, then data will be provided only as listings.
- All analyses will be performed using SAS® Software version 9.4 or later (SAS Institute, Inc., Cary, NC).

6.2 Handling of Missing Data

All statistical analysis on the endpoints will be performed using only those patients with available data required for endpoint analysis. No missing value imputation will be performed unless otherwise specified.

7. SUMMARY OF BASELINE INFORMATION

7.1 Patient Enrollment and Accountability

Patient disposition including numbers and percentages will be summarized. A patient level listing will also be provided.

7.2 Demographics and Baseline Characteristics

Patient demographics, age, sex, race, and other demographic variables are summarized descriptively. For baseline characteristics, efficacy/safety measures that describe the disease characteristics at baseline are summarized descriptively. The measures to be summarized depend on the study indication and measures collected at screening and/or baseline.

7.3 Medical History and Prior Intervention

	Revision Date: January 22, 2019		Rev	For Use Only by Affiliates of Edwards Lifesciences	Page 17 of 25
	Title		Statistical Analysis Plan for Edwards CLASP TR EFS		

Following medical history and prior intervention will be summarized by number and percentage. Other medical history and prior intervention variables may be added as deemed necessary.

7.3.1 Cardiovascular Risk Factors

- Number of hospitalizations for heart failure in the last 12 months
- Number of days hospitalized for heart failure in the last 12 months
- Angina
- Aneurysm
- Atrial Flutter/Fibrillation
- Flutter/Fibrillation Ablation
- Ventricular Tachyarrhythmia
- Conduction Defects/Heart Block
- Congestive Heart Failure (CHF)
- Atrial Septal Defect (ASD)
- Ventricular Septal Defect (VSD)
- Carotid Artery Stenosis
- Carotid Surgery
- Carotid Intervention
- Cardiogenic Shock

	Revision Date: January 22, 2019		Rev		For Use Only by Affiliates of Edwards Lifesciences	Page 18 of 25
	Title	Statistical Analysis Plan for Edwards CLASP TR EFS				

- Coronary Artery Disease (>50 Stenosis)
- Deep Vein Thrombosis (DVT)
- Dyslipidemia or Hyperlipidemia
- Endocarditis
- Hypertension
- Hypotension
- Myocardial Infarction (MI)
- Peripheral Vascular Disease
- Rheumatic Heart Disease
- Stroke
- Transient Ischemic Attack (TIA)

7.3.2 Non-Cardiovascular Risk Factors

- Chronic Lung Disease
- COPD
- Asthma
- Pulmonary Hypertension
- Pulmonary Edema
- Pulmonary embolism
- Other pulmonary disease

 Edwards Lifesciences	Revision Date: January 22, 2019		Rev	For Use Only by Affiliates of Edwards Lifesciences	Page 19 of 25
	Title	Statistical Analysis Plan for Edwards CLASP TR EFS			

- Diabetes
- Thyroid Disease
- Renal Disease
- Gastrointestinal or esophageal bleeding
- Cirrhosis or other liver disease
- Other gastrointestinal or hepatobiliary conditions
- Cancer/Malignancy
- Coagulopathy
- Chronic Anemia
- Thrombocytopenia
- Dementia (including Alzheimer's)
- HIV/AIDS
- Patient immunocompromised
- Autoimmune Disorder
- Frailty
- Smoking
- Alcohol consumption

7.3.3 Prior Cardiovascular Interventions or Surgeries

- Pacemaker, ICD or CRT (cardiac resynchronization Therapy)

 Edwards	Revision Date: January 22, 2019		Rev	For Use Only by Affiliates of Edwards Lifesciences	Page 20 of 25
	Title	Statistical Analysis Plan for Edwards CLASP TR EFS			

- PCI/Stent
- Coronary Artery Bypass Graft (CABG)
- Prior Aortic Valve (AV) surgery/intervention
- Prior Mitral Valve (MV) surgery/intervention
- Prior Pulmonic Valve (PV) surgery/intervention
- Cardiac Transplant
- Other cardiovascular interventions or surgery

7.4 Procedural Information

Following procedural information will be summarized by mean and standard deviation for continuous variables and by counts and percentages for categorical variables.

- Skin incision to Femoral vein access closure time (min)
- Fluoroscopy Time (min)
- Volume of Contrast Used (ml)
- Implant Access Approach
- Device permanently implanted
- Device implanted as intended
- Reintervention Required
- Device Malfunction

 Edwards	Revision Date: January 22, 2019		Rev	For Use Only by Affiliates of Edwards Lifesciences	Page 21 of 25
	Title		Statistical Analysis Plan for Edwards CLASP TR EFS		

- Implant hospitalization length of stays: Days from index procedure to discharge of index procedure

8. STATISTICAL ANALYSIS OF STUDY ENDPOINTS

8.1 Safety and Performance Endpoints

Safety:

The safety endpoint for this clinical study is a composite endpoint of Major Adverse Events (MAEs) at 30 days. No hypotheses testing will be performed for this endpoint. MAE endpoint and its components will be summarized by counts, percentage and 95% Confidence Interval (CI) of the percentage for the ITT and AT population. CEC adjudicated data will be used in the analysis.

Performance:

All performance endpoints will be summarized by counts and percentage.

The device success endpoint will be evaluate for the ITT and AT cohorts, per device analysis.

The procedure success endpoint will be assessed for the ITT and AT cohort, per patient analysis. Only device-related intervention will be considered when calculating procedure success.

The clinical success endpoint at 30 days will be summarized for the ITT and AT cohort, per patient analysis. CEC adjudicated data will be used for MAEs.

Additional Safety Assessments at 30 days will be summarized by counts and percentages for the ITT and AT cohort.

In addition to the above assessments, a listing of all the AEs and SAEs for the ITT study population will be provided.

 Edwards Lifesciences	Revision Date: January 22, 2019		Rev	For Use Only by Affiliates of Edwards Lifesciences	Page 22 of 25
	Title		Statistical Analysis Plan for Edwards CLASP TR EFS		

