#### 11.5 Investigator AE Causality Assessment

Adverse events will be assessed by the Investigator for causality to the study device and index procedure. The relationship between the use of the study device and study/implant procedure and the occurrence of each adverse event will be assessed and categorized.

During causality assessment, clinical judgement shall be used and the relevant study documents (i.e. CIP, ICF, IFU and/or CIB) shall be consulted for the listing of foreseeable adverse events/potential risks. The presence of confounding factors, such as concomitant medication/treatment, the natural history of the underlying disease, other concurrent illnesses or risk factors shall also be considered.

- **Not related:** There is no relationship between the event and the device or implant procedure.
- **Unlikely:** The relationship with the use of the device seems not relevant and/or the event can be reasonably explained by another cause, but additional information may be obtained.
- **Possible:** The relationship with the use of the device is weak but cannot be ruled out completely. Alternative causes are also possible (e.g. an underlying or concurrent illness/ clinical condition or/and an effect of another device, drug or treatment). Cases

were relatedness cannot be assessed or no information has been obtained should also be classified as possible.

- **Probable:** The relationship with the use of the device seems relevant and/or the event cannot reasonably explained by another cause, but additional information may be obtained.
- **Related (Causal relationship):** The event is related to the device and/or procedure beyond a reasonable doubt.

\*Reference **Appendix A: Study Definitions** for the full causality definitions.

An adverse event can be related both to the study procedure and the study device. Complications of procedures are considered not related if the said procedures would have been applied to the patients also in the absence of study device use/application.

In some particular cases the event may not be able to be not adequately assessed because information is insufficient or contradictory and/or the data cannot be verified or supplemented. The Sponsor and the Investigators will make the maximum effort to define and categorize the event and avoid these situations.

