## 11.7 Sponsor Assessment and Reporting

The Sponsor is responsible for the classification and reporting of adverse events and ongoing safety evaluation of the clinical investigation in accordance with 21 CFR 812.

All AEs will be reviewed by the Sponsor's Clinical Safety department. Each AE will be assessed for seriousness, device and procedure relatedness, and whether it was anticipated or not anticipated (based on the list of potential risks provided in section 3.1). In case of disagreement between the Sponsor or CEC and the Investigator, the Sponsor will communicate both opinions to concerned parties, as necessary.

A summary of adverse events will be reported to the FDA annually in the Annual Progress Report (APR).

The Sponsor will also report any confirmed unanticipated adverse device effect (UADE) to FDA as soon as possible, but no later than 10 working days after first receiving notice of the effect.

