### Access Site

#### *(Sponsor Definition)*

Site of insertion of study device components.

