**Possible:** the relationship with the use of the investigational device is weak but cannot be ruled out completely. Alternative causes are also possible (e.g. an underlying or concurrent illness/ clinical condition or/and an effect of another device, drug or treatment). Cases where relatedness cannot be assessed or no information has been obtained should also be classified as possible.

**Probable:** The relationship with the use of the investigational device seems relevant and/or the event cannot reasonably explained by another cause, but additional information may be obtained.

**Related:** the serious event is associated with the investigational device or with procedures beyond reasonable doubt when:

- the event is a known side effect of the product category the device belongs to or of similar devices and procedures;
- the event has a temporal relationship with investigational device use/application or procedures;
- the event involves a body-site or organ that
  - the investigational device or procedures are applied to;
  - the investigational device or procedures have an effect on;
- the serious event follows a known response pattern to the medical device (if the response pattern is previously known);
- the discontinuation of medical device application (or reduction of the level of activation/exposure) and reintroduction of its use (or increase of the level of activation/exposure), impact on the serious event (when clinically feasible);
- other possible causes (e.g. an underlying or concurrent illness/ clinical condition or/and an effect of another device, drug or treatment) have been adequately ruled out;
- harm to the patient is due to error in use;
- the event depends on a false result given by the investigational device used for diagnosis, when applicable;

In order to establish relatedness, not all criteria listed above must be met at the same time, depending on the type of device, procedure and the serious event.

An adverse event can be related both to the study procedure and the study device. Complications of procedures are considered not related if the said procedures would have been applied to the patients also in the absence of investigational device use/application.

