
Procedural Success
 
Device success with evidence of a reduction in TR grade by at least one grade (scale: none/trace, mild, moderate, severe, massive, torrential) at end of procedure, and without the need for a surgical or percutaneous intervention prior to hospital discharge. Per patient analysis.

Prosthesis
 
An artificial substitute

Re-intervention (Sponsor Definition)
 
Any intervention on the previously implanted study device (repair, alteration or replacement)

---

Renal Complication (Long-Term)
 
Long-term Renal Complication is defined as onset of renal replacement therapy (i.e hemodialysis, renal transplant)

New need for renal replacement therapy (Sponsor Definition)
 
New need for renal replacement therapy (i.e hemodialysis, renal transplant)

Screen Failure
 
A patient who has signed the consent but, does not fulfill enrollment criteria: does not meet the inclusion criteria or who meets at least one of the exclusion criteria.

Septicemia (Sponsor Definition)
 
Systemic infection requiring hospitalization and treatment with antibiotics.

Serious Adverse Event (SAE) (FDA 21 CFR 812.3)
 
An adverse event that
 
 
• Results in death
 
• Is life-threatening
 
• Requires inpatient hospitalization or prolongation of existing hospitalization
 
• Results in persistent or significant disability/incapacity 
 
○ Is an important medical event which may jeopardize the patient, and may require medical or surgical intervention to prevent one of the above outcomes
 
 
 

Severe Bleeding (Sponsor Definition)
 
Severe bleeding is a fatal, life-threatening, extensive, or major bleeding, as defined by MVARC.

SF-36
 
A survey with 36 questions that results in two scales of mental and physical functioning and overall health related quality of life.
 
SF-12: A 12 question abridged and validated version of the SF-36

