3.2.2 Procedural Success

	Revision Date: January 22, 2019		Rev	For Use Only by Affiliates of Edwards Lifesciences	Page 9 of 25
	Title		Statistical Analysis Plan for Edwards CLASP TR EFS		

Device success with evidence of a reduction in TR grade by at least one grade (scale: none/trace, mild, moderate, severe, massive, torrential) at end of procedure, and without the need for a surgical or percutaneous intervention prior to hospital discharge. Per patient analysis.

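### SAP 8.1 counts only device-related intervention in procedural success, a limit absent from the endpoint's definition in SAP 3.2.2 and the protocol; SAP 8.2.2 also words the re-intervention rate differently from the defined endpoint

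*SAP*

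**What the plan says.** **Procedural success.** SAP 3.2.2 sets three conditions per patient: device success, a fall in TR of at least one grade at the end of the procedure, and a course "without the need for a surgical or percutaneous intervention prior to hospital discharge". The protocol uses the same clause in the synopsis, in section 5.2.2 and in Appendix A. None of the four places limits the intervention by cause. Protocol 12.4.2 says only that the endpoint is analysed per patient. SAP 8.1, which sets the calculation, says: "Only device-related intervention will be considered when calculating procedure success".

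**Clinical success.** SAP 3.2.3 and protocol 5.2.3 build it on procedural success, adding freedom from MAEs at 30 days. SAP 8.1 adds: "CEC adjudicated data will be used for MAEs".

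**Re-intervention.** SAP 3.3.2 item C and protocol 5.3.2 item C define the endpoint as unplanned or emergency re-intervention, by either route, related to the device. Protocol 12.5 asks for that rate at the pre-specified follow-up periods. SAP 8.2.2 instead tabulates re-intervention rates for tricuspid regurgitation at 30 days, 6 months, 1 year and annually thereafter. Protocol Appendix A defines re-intervention as "Any intervention on the previously implanted study device (repair, alteration or replacement".

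**The concern.** The SAP contains a definition and a calculation rule that classify some patients differently. A patient with device success and a TR reduction who has a non-device-related surgical or percutaneous intervention before discharge fails under 3.2.2 and succeeds under 8.1. An analyst following 8.1 would report a figure under the name procedural success that is not the endpoint the protocol defines.

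The study is descriptive, so no alpha, power or decision rule is at stake. But in an early feasibility study meant to guide later trial designs, the percentage is the result. A reader who takes it with the protocol definition would be reading a different quantity.

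The re-intervention wording raises a similar problem. The SAP line drops the unplanned-or-emergency condition and may add a limit by indication, so the tabulated event may not be the defined endpoint.

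**Working it through.** The documents state no expected rate for these endpoints, so there is no figure to reproduce. The check compares the rules and then sizes the gap per patient.

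**Step 1: direction of the difference in procedural success.** Among patients with device success and a TR reduction of at least one grade, let *I* be those with a surgical or percutaneous intervention before discharge, and *R* those whose intervention is device-related. *R* lies within *I*.
- SAP 3.2.2 success: not in *I*.
- SAP 8.1 success: not in *R*.
- Every 3.2.2 success is also an 8.1 success. The extra successes under 8.1 are the patients in *I* but not in *R*; call their number *k*.
- Rate under 8.1 minus rate under 3.2.2 = *k*/N, which is never negative.

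**Step 2: size.** *k* is not in the documents; 0 to 3 is assumed. N is up to 65 in protocol section 6 and 15 in SAP 2.2.

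| *k* (assumed) | N = 65 | N = 15 |
|---|---|---|
| 0 | 0 | 0 |
| 1 | 1/65 = 1.5 points | 1/15 = 6.7 points |
| 2 | 2/65 = 3.1 points | 2/15 = 13.3 points |
| 3 | 3/65 = 4.6 points | 3/15 = 20.0 points |

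Illustrations with assumed counts and the Clopper-Pearson intervals named in SAP 6.1:
- N = 65: 55/65 = 84.6% (95% CI 73.5 to 92.4) under 8.1. With *k* = 3, 52/65 = 80.0% (68.2 to 88.9) under 3.2.2.
- N = 15: 13/15 = 86.7% (59.5 to 98.3) under 8.1. With *k* = 1, 12/15 = 80.0% (51.9 to 95.7) under 3.2.2.

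Protocol 12.2.2 and SAP 4.2 make the as-treated set primary for performance. Patients counted in *k* have device success, so they would ordinarily belong to that set, and the same *k* is divided by a smaller N. If, for example, 60 of 65 or 13 of 15 were implanted (assumed), one patient is worth 1/60 = 1.7 or 1/13 = 7.7 points.

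**Step 3: clinical success.** The gap is the number of those *k* patients with no MAE at 30 days, divided by N. A patient whose intervention was for a major access-site complication fails clinical success under both rules, because that complication is itself an MAE component. The clinical success gap is therefore at most *k*/N.

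**Step 4: re-intervention.**

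| Condition | SAP 3.3.2 C; protocol 5.3.2 C and 12.5 | SAP 8.2.2 |
|---|---|---|
| Unplanned or emergency | required | not stated |
| Related to the device | required | not stated in the line; Appendix A makes re-intervention an intervention on the implant |
| For tricuspid regurgitation | not required | stated |

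Read literally, a planned re-intervention for TR counts only under 8.2.2, and an unplanned device-related one for another reason counts only under the definition. The time points are 30 days, 6 months and years 1, 2, 3, 4 and 5, which makes 7. SAP 8.1 tabulates the defined event at 30 days as an MAE component. Later it appears in SAP 8.2.2 only inside the MAE composite, with no component rates specified. On this reading 7 − 1 = 6 time points lack a separate rate.

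**The case against.** **SAP 8.1 may be a sensible operational rule.** Taken literally, the 3.2.2 clause also fails a patient for an intervention remote from the valve, and a sponsor could reasonably wish to exclude that. This stands as a reason for the sponsor to choose. It does not remove the conflict, because the rule changes who is a success and none of the four definitions carries it.

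**The SAP was written for protocol version A, and the protocol supplied is version C.** This does not explain either mismatch: 3.2.2 against 8.1, and 3.3.2 C against 8.2.2, both lie within the SAP.

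**The 8.2.2 line may be shorthand.** The Appendix A definition already ties re-intervention to the implant, and the reference to tricuspid regurgitation may simply name the study indication. SAP 9.2 also reports percentages of patients with early and late adverse events. Much of this stands, which is why that part is held with moderate confidence. What remains is the missing unplanned-or-emergency condition and a possible indication limit. The MAE paragraph of the same section uses the full wording, and SAP 9.2 does not name re-intervention.

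**Stronger readings the documents do not support.** A reader might infer that the device-related filter cannot be applied at all, since five causality grades exist with no cut-off and protocol 11.7 settles disagreement only by this: "In case of disagreement between the Sponsor or CEC and the Investigator, the Sponsor will communicate both opinions to concerned parties, as necessary". That sentence concerns safety reporting, not endpoint derivation. The CEC Charter, which holds CEC procedures and definitions and prevails over the protocol, is not among the documents, so a gap cannot be asserted. A reader might also ask whether minor access-site complications are MAEs. The component is worded as major in protocol 5.1, in Appendix A and in SAP 3.1, and the question does not bear on this point.

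**Conclusion.** The procedural success conflict holds with high confidence. SAP 8.1 applies a limit that the endpoint's definition does not contain, and the resulting rate is equal to or higher than the defined one. The direction follows from the two rules alone. The size depends on a count the documents do not give: 0 to 3 affected patients, an assumed range, means 0 to 4.6 points at 65 patients or 0 to 20.0 points at 15. It would be wrong to infer that reported success will be materially inflated, because the effect may be zero.

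The re-intervention mismatch holds with moderate confidence. The wordings differ, and on a literal reading the defined endpoint has no separate rate in the SAP after 30 days. It would go too far to say the SAP abandons the endpoint: 3.3.2 C still lists it, it is counted at 30 days, and it stays inside the later MAE composite.

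Both matters affect what descriptive percentages mean. Neither touches a test, alpha or power.

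**What to change.** 1. In SAP 8.1, report procedural success, and the clinical success built on it, by the 3.2.2 definition. Show the device-related version as a labelled secondary line.
2. If the sponsor intends the narrower endpoint, amend the protocol synopsis, protocol 5.2.2, Appendix A and SAP 3.2.2 instead, so that all the passages agree.
3. In SAP 8.2.2, use the 3.3.2 C wording and report that rate separately at 30 days, 6 months and 1 to 5 years.

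Items 1 and 3 are SAP text changes that need no new data collection. The cost of item 1 is that the reported success rate may be lower, and that the unqualified clause also counts interventions remote from the valve. The secondary line lets readers see how much of any difference comes from those. Item 2 requires a protocol amendment.
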